Study Title: To Determine the Economic and Functional Impact of Peri-Operative Extension Assist Pneumatic Bracing for Primary Total Knee Arthroplasty (TKA) Non-Inferiority Trial

Study Sponsor:

Ongoing Care Solutions, Inc.

Project contact: [name], Vice President of Ongoing Care Solutions, Inc.

[name]

[name]

[contact] (Ph)

[contact] (F)

Principal Investigator: [name]

Regulatory Sponsor:

This study is an investigator initiated research trial. The study site will be considered its own regulatory sponsor and is responsible for internal data monitoring and any study reporting required by ClinicalTrials.gov.

Background and Significance

Knee osteoarthritis (OA) is increasing in the United States rapidly due to increased lifespan and obesity. The use of unloader bracing has been proposed as an adjunct to current treatments. While the use of an unloader brace has not been shown to be beneficial for patients with Kellgren-Lawrence grade 1 and 2 osteoarthritis [1], unloader braces have shown benefits in patients with end-stage osteoarthritis, Kellgren-Lawrence grade 3 and 4. These benefits include increased time to total knee arthroplasty (TKA) and lower number of injections [2]. Indeed, pneumatic unloader knee bracing has also been shown to increase strength and function of these patients with end-stage knee OA [3]. Typically, the next step for end-stage knee OA is a TKA where OA accounts for 94-97% of TKAs [4,5].

While bracing has been shown to be beneficial for patients with OA in terms of function and strength, whether these unloader braces are also similarly beneficial after surgery needs to be examined. Therefore we questioned whether wearing a brace that has previously been shown to increase strength and function in OA patients can also increase strength and function in patients after TKA.

The primary objective of this study is to determine the efficacy of bracing in improving function and rehabilitation prior to and after TKA.

Additional goal of the study is to assess time taken to normalized function after TKA and its impact on cost. Secondary objectives are to quantify and observe pain medication use, swelling, muscle strength and girth, and gait efficiency.

Study Design

Methods

This a randomized, standard of care controlled study.

Sample

Potential subjects will be recruited from a pool of TKA patients presenting to Cleveland Clinic orthopedic providers at main campus that may benefit from using a knee brace.. This study aims to complete follow-up with 40 patients. 20 out of 40 patients will receive adjunct therapy using the OCSI brace. Patients will be allocated to one of these two groups via computer randomization. The PI ([name]) will be blinded to patient compliance and evaluation during data acquisition and statistical analysis. All study patients will receive standard of care therapy (pain medications, and other modalities as needed). At home physical therapy will occur at standard of care scheduled intervals. Once physical therapy begins at Cleveland Clinic, patients in both the control and brace group will receive outpatient Physical Therapy 2 times a week for two weeks, then the number of physical therapy visits will be at the discretion of the clinician.

Patient selection:

- Age: 50 or older

- Radiographic: Varus or valgus knee deformity less than 10 degrees
- BMI of 40 or less

Research Procedures

Visit 0: Potential patients will be consented during their office visit with [name]. Once consented, patients will be computer randomized into either the knee brace group or the control group. For the knee brace group, measurements will be taken during the clinic visit, an order will be written for the brace and sent to Hanger Clinic where they will be in contact with the study participant to schedule the brace fitting. The subject can start wearing the brace at this time until surgery.

Visit 1 (6 weeks prior to surgery): Participant will meet with study coordinator and complete both questionnaires and physical tests.

Visit 2 (1 week prior to surgery): Participant will meet with study coordinator and complete both questionnaires and physical tests.

Visit 3 (1 week after surgery): Participant will meet with study coordinator and complete both questionnaires and physical tests. The brace will NOT be worn until after staple removal (10 to 14 days after surgery).

Visit 4 (6 weeks after surgery): Participant will meet with study coordinator and complete both questionnaires and physical tests.

Visit 5 (12 weeks after surgery): Patient will meet with study coordinator and complete both questionnaires and physical tests. At this point, the study time points are complete and the brace no longer needs to be worn for the study.

Chart review: At 9 months, the study team will review participant’s chart for pain medication utilization and number of physical therapy visits during the study.

	Visit 0 Office visit (scheduling surgery)	Visit 1 6 weeks prior to surgery (±4 weeks)	Visit 2 1 week prior to surgery (±1 week)	Visit 2 1 week after surgery (±1 week)	Visit 3 6 weeks after surgery (±2 weeks)	Visit 4 12 weeks after surgery (±2 weeks)	9 months After surgery (chart review)
Informed Consent	X						
Randomization	X						

Timed up and go (TUG) test		X	X	X	X	X	
Timed stair-climb test		X	X	X	X	X	
Single-limb stance time (bilateral)		X	X	X	X	X	
6 minute walk test		X	X	X	X	X	
AROM, PROM		X	X	X	X	X	
Knee Society objective score		X	X	X	X	X	
Knee Society functional Score		X	X	X	X	X	
KOOS (Jr)		X	X	X	X	X	
HSS scale		X	X	X	X	X	
Pain score on visual analog scale (rest)		X	X	X	X	X	
Pain score on visual analog scale (activity)		X	X	X	X	X	
Pain medications utilization		X	X	X	X	X	X
Number of therapy visits							X

- For this research study, we will ask you to fill out some additional physical tests will be performed. These tests include:
 - Timed up and go (TUG) test: standing up from seated position and walking to a designated line, walking back, and returning to seated position
 - Timed stair-climb test: walking up and down stairs
 - Single-limb stance time (bilateral): standing on one leg unassisted

- 6 minute walk test: distance walked in 6 minutes
- Patient reported outcomes will also be assessed using multiple validated questionnaires
 - Knee Society Score (KSS)
 - Knee Injury and Osteoarthritis Outcome Score (KOOS Jr)
 - HSS scale
 - Visual Analog Scale (Pain score)

Participant Compliance

Study participants will be given a pedometer and notebook supplied by the sponsor to record daily steps. This will be used to monitor compliance with physical therapy and the use of the brace as it is expected there should be increased activity over time.

Data Analysis

Descriptive statistics (mean, standard deviation, and coefficient of variation) will be used to compare the demographics between the two cohorts. Functional metrics will be compared pre- and post-surgery at 0- and 3- months. Unless otherwise indicated, all testing of statistical significance will be two-sided, and a difference resulting in a p-value of less than or equal to 0.05 will be considered statistically significant. Also, after each analysis, General Linear Models (GLM) will be used to control for possible confounders, including BMI, gender, age, and ethnicity.

Adverse Events and Data Monitoring Committee

Procedural safety will be documented in this study through patient and surgeon reported adverse events. ARs will be documented for all ceases in this study.

An unanticipated problem involving risks to participants or others is any event that (1) is unforeseen, (2) caused harm or placed a person at increased risk of harm, and (3) is related to the research procedures.

An Adverse Event (AE) is any untoward or unfavorable medical occurrence, including any abnormal sign (for example, abnormal physical exam or laboratory finding), symptoms, or disease. Adverse events can encompass both physical and psychological harms.

An Internal Adverse Event (AE) is an untoward medical occurrence, which occurs to participants in research conducted by Cleveland Clinic and/or Cleveland Clinic is the IRB of record.

External Adverse Event (AE) is an untoward medical occurrence experienced by subjects enrolled at other institutions for the same study approved at Cleveland Clinic or a different study using the same study drug/device.

A Serious Adverse Event (SAE) is any adverse experience that results in any of the following outcomes:

- Death

- A life-threatening experience
- Inpatient hospitalization or prolongation of existing hospitalization
- A persistent or significant disability/incapacity
- A congenital anomaly/birth defect
- Important medical events that may not result in death, be life-threatening, or require hospitalization may be considered a serious adverse experience when, based upon appropriate medical judgment, they may jeopardize the patient or subject and may require medical or surgical intervention to prevent one of the outcomes listed in this definition.

An Unexpected Adverse Event means any AE not previously known or included in the consent form or other risk information.

Related/Possibly Related means there must be reasonable evidence to suggest the event was caused by the device or investigational intervention.

- 1) Internal Serious Adverse Events (events that occur to participants enrolled in research being conducted by Cleveland Clinic and when Cleveland Clinic is the IRB of record) must be promptly reported to the IRB using the IRB AE report form within 10 working days from discovery/awareness which meet any of the following criteria as assessed by the PI/Co-I:
 - a. Serious, unexpected, and related/possibly related
 - b. AEs determined to be occurring at a significantly higher frequency or severity other than expected
 - c. Other unexpected AE's, regardless of severity, that changes the risk benefit ration of the study and results in changes to the Research protocol or Informed Consent process/document
 - d. All internal SAEs are also reported at continuing review using the AE Summary Log
- 2) External Serious Adverse Events (events experienced by subjects enrolled at other institutions for the same study approved at Cleveland Clinic or a different study using the same study device/drug) are reportable to the IRB using the IRB AE Report Form within 10 working days from discovery/awareness when:
 - a. The External SAE report includes reasonable evidence as assessed by a central monitoring entity [Coordinating or Statistical Center, or a Data Safety Monitoring Board (DSMB) or Data Monitoring Committee (DMC)] that the event is Serious, Unexpected, and Related/Possibly Related AND places the subjects or others at a greater risk of physical or psychological harm than was previously known or recognized. This will require a change in the protocol and/or consent document.
 - b. External SAE reports provided by the Sponsor to the investigator indicating the event is Serious, Unexpected and Related/Possibly related but without reasonable evidence or DSMB/DMC determination of greater risk are not reportable to the IRB within the 10 day window. Without Sponsor evidence or assessment the implications of the event cannot be determined by the research team and therefore

need not be reviewed. These SAE' shall be placed on the AE Summary log to be submitted at the annual continuing renewal.

- 3) DEATHS are to be reported to the IRB using the IRB AE Report Form according to the following guidelines:
 - a. Internal Death
 - i. Related/possibly related whether expected or unexpected– within 5 working days from discovery/awareness
 - ii. not related and expected – at time of continuing review
 - iii. Not related and unexpected – at time of continuing review except cancer studies
 - b. External Death
Related/possibly related and unexpected – within 5 working days from discovery/awareness not related whether expected or unexpected – at time of continuing review related/possibly related and expected – at time of continuing review
 - c. ALL Deaths are also reported at time of continuing review using the AE summary log.
- 4) Non-serious Adverse events (Internal and External) that are both Related/Possibly related and unexpected are reported on the AE Summary Log at time of continuing review to assess trends.
- 5) An IRB staff (a qualified, licensed practitioner assigned to this function by the IRB chair and IRB Executive Director) reviews Adverse Event Reports to determine whether they represent Unanticipated Problem Involving Risks to Participants or Others. Events that are assessed, by either the IRB Staff or Investigator, to place subjects or others at a greater risk of harm than was previously known or recognized, or changes the risk/benefit ratio of the study, or requires a change in the protocol and/or consent document are referred to Full Board for review under Policy #70.
- 6) Events that do not involve risk to Participants or Others or changes to the informed consent or protocol do not require further review. Investigators are informed of the determination and the IRB file is updated.
- 7) The AE Summary Log is reviewed by the IRB at the time of continuing review to identify trends in frequency and severity which may impact subject safety.

This study is an Investigator Initiated research trial. Each study site will be considered its own regulatory sponsor and is responsible for internal data monitoring and any study reporting required by ClinicalTrials.gov.

References:

- 2) Chughtai M, Bhave A, Khan SZ, Khlopas A, Ali O, Harwin SF, Mont MA. “Clinical Outcomes of a Pneumatic Unloader Brace for Kellgren-Lawrence Grades 3 to 4 Osteoarthritis: A Minimum 1-Year Follow-Up Study.” *J Knee Surg*; 29(8):634-638.

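### The title promises a non-inferiority trial, but the plan asks whether the brace improves function and gives no margin, confidence-interval rule or clear between-arm contrast

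*Combined protocol and SAP*

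**What the plan says.** The Study Title ends "Pneumatic Bracing for Primary Total Knee Arthroplasty (TKA) Non-Inferiority Trial". This is the only mention of non-inferiority in the document.

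The rest of the plan is framed as a search for benefit:

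- Background and Significance asks whether the brace "can also increase strength and function in patients after TKA".
- The same section states: "The primary objective of this study is to determine the efficacy of bracing in improving function and rehabilitation prior to and after TKA".
- Study Design, Methods states: "This a randomized, standard of care controlled study".
- Sample states: "This study aims to complete follow-up with 40 patients". It adds "20 out of 40 patients will receive adjunct therapy using the OCSI brace" and "All study patients will receive standard of care therapy". The brace is therefore an addition to standard care, not a replacement for part of it.

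Data Analysis states: "Functional metrics will be compared pre- and post-surgery at 0- and 3- months". It then sets two-sided testing with significance at p ≤ 0.05 as the default, followed by general linear models that adjust for BMI, gender, age and ethnicity. The default allows for exceptions, but none is given.

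**The concern.** A non-inferiority trial asks whether a treatment is worse than its comparator by no more than a stated amount. It needs that amount (the margin) and a rule that sets a confidence limit against it. This plan has the name and neither component.

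The label matters most when the result is null. In a superiority trial, p > 0.05 is inconclusive. Under a non-inferiority title, the same p-value can be presented as showing that the brace is no worse. With 20 patients per arm that inference would be unsound, because the data would usually be compatible with a sizeable true deficit.

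**Working it through.** **1. The passages side by side.**

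| Element | What the document gives |
|---|---|
| Design label | Non-inferiority (Study Title only) |
| Research question and primary objective | Improvement in function (Background and Significance) |
| Role of the brace | Add-on to standard care (Sample) |
| Inferential rule | Two-sided test of a difference, p ≤ 0.05 (Data Analysis) |
| Margin, non-inferiority hypothesis, CI rule | None |
| Between-arm contrast for functional metrics | Not clearly stated; the text speaks of before and after surgery |

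The p ≤ 0.05 rule is direction-neutral. The superiority intent comes from the research question and objective, not from the test.

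**2. What each result could support.** Suppose the test is applied between arms. A significant result in favour of the brace would show superiority, and so imply non-inferiority for that outcome. For any other result, non-inferiority depends on whether the CI excludes a prespecified margin. No margin exists, so the step cannot be taken.

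**3. Inputs for the size of the problem.** From the document: 40 completers, 20 of them braced, so 20 per arm; two-sided alpha 0.05. Assumed: an unadjusted two-sample t-test between arms on one outcome. The document gives no SD, effect, margin or power, so the figure of 40 cannot be reproduced, and everything below is in SD units.

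**4. Precision.**
- Standard error of the difference = √(2/20) = 0.316 SD; df = 20 + 20 − 2 = 38.
- 95% CI half-width = t(0.975, 38) × 0.316 = 2.024 × 0.316 = 0.640 SD.
- An observed difference of exactly zero would have a CI from −0.64 to +0.64 SD.

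**5. Chance of p > 0.05 when the brace is truly worse.** With F the noncentral t distribution function on 38 df and noncentrality δ/0.316, P(p > 0.05) = F(2.024) − F(−2.024).

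| True difference δ | Noncentrality | P(p > 0.05) |
|---|---|---|
| −0.3 SD | −0.949 | 0.848 |
| −0.5 SD | −1.581 | 0.662 |
| −0.8 SD | −2.530 | 0.307 |

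Simulation with 400,000 trials per setting gave 0.849 and 0.662 for the first two rows.

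**6. What 40 patients could do if non-inferiority were intended.** With margin M and true benefit δ, power at one-sided 0.025 is 1 − F(2.024) with noncentrality (M + δ)/0.316. It reaches 80% when M + δ = 0.909 SD.
- δ = 0: M = 0.909 SD.
- δ = 0.3 SD: M = 0.909 − 0.3 = 0.609 SD.
- δ = 0.5 SD with M = 0.5 SD: M + δ = 1.0 SD, power about 87%.

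The supportable margin therefore depends on the true difference assumed. No single figure can be quoted without it.

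**The case against.** The strongest reply is that this is one stray word in a title. Everything after it is consistent with an improvement question, and the document never says that p > 0.05 will count as non-inferiority. That is correct. A reader might infer that the trial plans to declare non-inferiority from a null p-value; no text supports this. What stands is that the label and the analysis disagree, and that nothing in the plan blocks the misreading.

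A second reply is that the label may have a purpose. The title covers economic as well as functional impact, Background and Significance has a cost goal, and the 9-month chart review collects therapy visits and pain medication use. Function no worse at lower resource use would be a coherent non-inferiority question. The document does not state it, but only the sponsor can rule it out, so a route that keeps non-inferiority is offered in the fix.

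Three further inferences should be resisted:

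- *Two-sided testing is the fault.* It is not. A two-sided 95% CI set against a stated margin would be acceptable.
- *A non-significant result can never support non-inferiority.* It can, if the CI excludes a prespecified margin. The limitation belongs to this plan.
- *The 40 patients were chosen without a power calculation.* The document gives none, but its silence does not show that none was made.

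Finally, covariate adjustment could narrow the interval below the unadjusted 0.64 SD. That is fair, but adjustment cannot supply a missing margin.

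**Conclusion.** The concern holds as an inconsistency in the current text. The title claims a design property that the plan does not have, and under the plan as written a result not significantly better for the brace cannot support non-inferiority.

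The numbers show why the misreading would matter: a moderately worse brace would escape a significant difference in most trials of this size. They rest on a between-arm reading of Data Analysis, 20 completers per arm, no covariate adjustment, and deficits assumed in SD units. The textual conclusion needs none of these assumptions.

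This should be fixed, but it does not invalidate the trial: the stated objective can be pursued without the label.

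**What to change.** The sponsor should make the label and the analysis agree before outcome data are seen.

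**Option A, which matches the stated objective.** Delete the non-inferiority label from the title and add to Data Analysis:

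> For each functional metric, the brace-minus-control difference will be reported with its 95% CI at the planned time points, including 12 weeks, with the direction favouring the brace stated. A p-value above 0.05 will be reported as inconclusive, not as evidence of non-inferiority or equivalence. With 20 per arm the unadjusted 95% CI half-width is about 0.64 SD.

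This also supplies the between-arm contrast. It does not choose a primary outcome, which is a separate matter. It needs no extra patients or procedures. The cost is that the sponsor gives up a label the plan does not support and says openly that the estimate will be imprecise.

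**Option B, only if non-inferiority is intended.** Prespecify one endpoint and time point, a justified margin and a CI rule. State the power of 40 patients for that margin together with the true difference assumed. If that difference is zero, 80% power at one-sided 0.025 needs a margin of about 0.91 SD; a smaller margin suffices at this size only if a true benefit is assumed. The cost is the work of justifying the margin and, if the power at 40 proves too low, more patients.

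### No baseline score taken before brace wear and before allocation is assured, and the analysis does not name the pre-surgery visit it uses

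*Combined protocol and SAP*

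**What the plan says.** All references are to the combined protocol and SAP.

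- **Order of events (Research Procedures, Visit 0).** "Once consented, patients will be computer randomized into either the knee brace group or the control group". The brace is then ordered from an outside clinic, and "they will be in contact with the study participant to schedule the brace fitting". No fitting date is given. On wear: "The subject can start wearing the brace at this time until surgery".
- **First tests.** "Visit 1 (6 weeks prior to surgery): Participant will meet with study coordinator and complete both questionnaires and physical tests". The schedule of assessments marks only consent and randomisation at Visit 0; every test and questionnaire starts at Visit 1.
- **Windows (schedule of assessments).** "Visit 1 6 weeks prior to surgery (±4 weeks") and "Visit 2 1 week prior to surgery (±1 week"). The schedule uses the label Visit 2 twice; here Visit 2 means the visit one week before surgery.
- **Analysis (Data Analysis).** "Functional metrics will be compared pre- and post-surgery at 0- and 3- months". Then "General Linear Models (GLM) will be used to control for possible confounders, including BMI, gender, age, and ethnicity". The covariate list is open-ended, but a baseline function score is not on it.

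**The concern.** The brace arm may start treatment before anyone has measured function. Nothing links fitting to Visit 1, so some brace patients could be tested before first wear and others after several weeks of it. Visit 2 falls at the end of the permitted wear period, so a score from that visit can carry brace effect in one arm only.

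Data Analysis relies on a comparison of pre-surgery with post-surgery values, yet the 0-month point is not tied to a scheduled visit. The text also does not say whether the arms are compared on change, compared at each time, or examined within arm. If change from an already-treated score is compared between arms, part of a real effect is subtracted away. Background and Significance cites gains in strength and function with this type of brace in end-stage osteoarthritis, so on the authors' own premise some effect before surgery is plausible. The primary objective also covers function before surgery, and without an assured pre-brace score the gain during pre-operative wear cannot be reliably measured.

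A second issue is that Visit 1 follows open allocation. Effort-dependent tests and questionnaires taken there may reflect the patient's knowledge of the arm even if the brace has not yet been worn.

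**Working it through.** **Nothing to reproduce.** The plan gives 40 completers, 20 per arm, and a two-sided 0.05 level, but no effect size, SD, power or margin. The check therefore has two parts: the timing, which rests on the documents, and an illustration, which rests on stated assumptions.

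**1. Timing**

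- Visit 1: 6 ± 4 weeks, so 10 to 2 weeks before surgery.
- Visit 2: 1 ± 1 week, so 2 to 0 weeks before surgery.
- Permitted wear before Visit 1 = max(0, L − d − v), where L is the interval from Visit 0 to surgery, d the fitting delay and v the weeks before surgery at which Visit 1 takes place. L and d are not in the documents. Assuming d = 2:

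| L (weeks, assumed) | Visit 1 at 6 weeks | Visit 1 at 2 weeks |
|---|---|---|
| 4 | not feasible | 0 |
| 6 | 0 | 2 |
| 8 | 0 | 4 |
| 10 | 2 | 6 |
| 12 | 4 | 8 |

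Wear before Visit 1 is therefore possible but not certain. At the nominal 6 weeks it is zero for the 6- and 8-week intervals. Wear before Visit 2 is permitted whichever way Visit 1 and fitting are ordered.

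**2. What a treated baseline does**

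Let D be the brace effect at 12 weeks in SD units, f the share of D already in the score used as baseline (it differs between Visit 1 and Visit 2), and r the pre/post correlation, with equal SDs.

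- Arms compared at 12 weeks only: estimate D, SD 1, for any f.
- Change score: estimate D(1 − f), SD √(2(1 − r)).
- ANCOVA: estimate D(1 − r×f), residual SD √(1 − r²).

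Assumed, not in the documents: D = 0.909, set so that the unadjusted t-test (38 df) has 80% power with 20 per arm; r from 0.3 to 0.7; f of 0, 25 or 50%.

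Example at r = 0.5, f = 50%: the change estimate is 0.909 × 0.5 = 0.455 with SD √(2 × 0.5) = 1. The ANCOVA estimate is 0.909 × (1 − 0.25) = 0.682 with residual SD √0.75 = 0.866.

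| r | Change score, f = 0/25/50% | ANCOVA (simulated), f = 0/25/50% | No baseline |
|---|---|---|---|
| 0.3 | 66/43/22% | 82/76/67% | 80% |
| 0.5 | 80/56/29% | 89/79/65% | 80% |
| 0.7 | 95/77/44% | 97/89/69% | 80% |

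The simulation includes the extra standard error caused by the baseline difference between arms. The simple formula ignores it and runs higher (at r = 0.5, f = 50%: 68% against 65%). By simulation, ANCOVA on the treated score falls below the unadjusted 80% once f exceeds about 12%, 24% and 38% at r = 0.3, 0.5 and 0.7.

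**3. What lost wear would cost**

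The smallest D at which ANCOVA on a clean baseline still has 80% power (by formula) is 0.868, 0.788 and 0.650 at r = 0.3, 0.5 and 0.7. Relative to 0.909 the tolerable loss is 1 − 0.868/0.909 = 4.5%, 1 − 0.788/0.909 = 13.3% and 1 − 0.650/0.909 = 28.5%. A fix that shortens wear enough to reduce D by more than this gives back the precision it gained.

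**The case against.** The strongest reply is that randomisation protects the trial. Allocation precedes all wear, so the difference between arms at 12 weeks is unbiased however much brace effect the pre-surgery scores contain, and pre-operative wear is deliberately part of the treatment. That stands. What it does not settle is that the plan never commits to that comparison, and its wording points to one that uses pre-surgery scores.

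A second reply is that f may be small. That also stands. At Visit 1 it could be zero for many patients. Background and Significance reports benefit in unoperated knees but says benefit after surgery is still to be examined, and wear stops until staple removal, 10 to 14 days after surgery. The documents support some effect before surgery, not any particular share of the 12-week effect.

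A reader might go further and infer that the baseline is contaminated in every brace patient, or that the trial's power is 29%. The documents support neither. The first would need a fitting date before Visit 1. The second needs a change-score analysis, r = 0.5 and f = 50% together, none of which the plan states. At r = 0.7 and f = 25%, ANCOVA on the treated score has 89% power, better than using no baseline.

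**Conclusion.** The point holds as a gap in sequencing and definition: the plan neither secures nor names a score taken before brace wear and before allocation. This follows from the visit text and schedule alone and does not depend on any assumed number.

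The consequence depends on the analysis. It is nil for bias in a plain 12-week comparison, a full loss of f in a between-arm comparison of change, and a loss of r×f under ANCOVA. A treated score is clearly possible if Visit 2 is the pre-surgery value, and possible, with unknown frequency, if Visit 1 is. The powers in the working show direction and scale only, because f, r and D are all assumed. What can be said more firmly is that, with 20 per arm, an untreated baseline covariate is worth having: under the same assumptions it raises power from 80% to between 82% and 97% by simulation, provided the brace effect itself is not reduced. The plan should be changed, but the gap does not invalidate the randomised comparison.

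**What to change.** Take the baseline questionnaires and physical tests before randomisation, in one of two ways.

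1. **Move the Visit 1 tests to Visit 0, ahead of randomisation.** No extra session and no wear lost. The cost is a longer Visit 0, and a baseline further from surgery wherever Visit 0 comes well before the present Visit 1.
2. **Keep the tests at Visit 1 and randomise afterwards.** No extra session, but the brace order and fitting wait until then. If Visit 1 falls late in its window, under 2 weeks of pre-operative wear may remain, so Visit 1 should be booked early.

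At minimum, complete the Visit 1 tests before the brace is handed over, agree this with the fitting clinic, and record the hand-over date. This still leaves a baseline taken with allocation known, and it can shorten wear.

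Under any option, name that score as the baseline in Data Analysis and state that Visit 2 is not the baseline. Reordering Visit 1 and fitting does nothing for a Visit 2 score; only naming the baseline does. Compare the arms as randomised at Visit 2 and at 12 weeks, with the named score as a covariate in the general linear model. The Visit 2 comparison then addresses the pre-surgery part of the primary objective.

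The change needs a protocol amendment and, for option 2 or the minimum version, coordination with the outside clinic. No patients are added.

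### The ±1 week window on the 1-week post-operative visit runs from the day of surgery to day 14 and overlaps the return to the brace, which adds avoidable noise and leaves brace status unclear at that visit

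*Combined protocol and SAP*

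**What the plan says.** The schedule table under Research Procedures heads the first post-operative column "Visit 2 1 week after surgery (±1 week") and marks every functional test, knee score and pain measure in it. The visit list in the same section describes the same assessment under a different number and without a window: "Visit 3 (1 week after surgery): Participant will meet with study coordinator and complete both questionnaires and physical tests". It then adds: "The brace will NOT be worn until after staple removal (10 to 14 days after surgery").

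On allocation, the Sample section says "20 out of 40 patients will receive adjunct therapy using the OCSI brace", so brace status is an issue for 20 patients.

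On analysis, the Data Analysis section says "Functional metrics will be compared pre- and post-surgery at 0- and 3- months" and that "General Linear Models (GLM) will be used to control for possible confounders, including BMI, gender, age, and ethnicity". It does not say which visit is the zero-month one.

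Nowhere do the documents require this visit to come before staple removal, say whether the tests are done with the brace on or off, or provide for recording or adjusting for the actual post-operative day.

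**The concern.** The text presents this as a visit before the brace returns, but the table's window lets it fall after that. It is the only post-operative assessment nominally placed before the brace is resumed. It is therefore the one point at which the effect of pre-operative bracing could be seen without post-operative bracing on top. It also feeds the stated goal of measuring time to normalized function.

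The window is loosest, relative to elapsed time, where recovery is likely to be fastest: ±1 week on 1 week is ±100%, against ±2 on 6 weeks (±33%) and ±2 on 12 weeks (±17%). A walk test on the day of surgery and one two weeks later measure different stages of recovery. With 20 patients per arm there is little precision to spare.

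**Working it through.** **Window.** Nominal day 7, tolerance 7 days (schedule table): 7 − 7 = 0 and 7 + 7 = 14. The permitted days are 0 to 14, or 15 calendar days.

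**Overlap with the brace's return.** Staple removal is on days 10 to 14 (visit list). The two ranges share days 10-14, or 5 of 15 permitted days (33%). This is a share of days, not of patients, because the brace returns only after each patient's own staple removal.

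**Share of brace-arm visits affected.** Assume that visit day is uniform on 0-14, removal day is uniform on 10-14, and the two are independent. There are 15 × 5 = 75 equally likely pairs.
- Visit strictly after removal: visit days 11, 12, 13 and 14 give 1 + 2 + 3 + 4 = 10 pairs. 10/75 = 13%, or 2.7 of 20.
- Counting the same day as well: 1 + 2 + 3 + 4 + 5 = 15 pairs. 15/75 = 20%, or 4 of 20.
- If all visits fall on days 7-14 (8 × 5 = 40 pairs): 10/40 = 25% to 15/40 = 38%, or 5 to 7.5 of 20.
- If all visits fall on days 5-9: 0%.

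At most 14 − 10 = 4 days of renewed wear could precede the visit.

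**Noise from timing.** The documents give no rate of recovery and no distribution of visit days, so both are assumed: a slope *b* of 0.5, 1 or 1.5 between-patient SD per week, and visit day uniform over the window. With the variance at a fixed day set to 1, timing adds *b*² × (width in weeks)²/12. The information lost is added/(1 + added).

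| Window | Variance of timing (weeks²) | *b* = 0.5 | *b* = 1 | *b* = 1.5 |
|---|---|---|---|---|
| Days 0-14 (2 weeks) | 4/12 = 0.333 | adds 0.083, loses 8% | adds 0.333, loses 25% | adds 0.75, loses 43% |
| Days 5-9 (4/7 week) | 0.327/12 = 0.027 | adds 0.007, loses 1% | adds 0.027, loses 3% | adds 0.061, loses 6% |

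For 20 patients per arm, days 0-14 give the precision of 20/1.083 = 18.5 down to 20/1.75 = 11.4 patients all seen on the same day. Days 5-9 give 20/1.007 = 19.9 down to 20/1.061 = 18.8.

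**Bias.** A difference between arms in mean visit day shifts the comparison by *b* × (days/7). A hypothetical 3 days gives 0.5 × 3/7 = 0.21 up to 1.5 × 3/7 = 0.64 SD. If the arms are seen on the same days on average, the shift is zero.

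**Which windows avoid the overlap.** ±2 days gives days 5-9, with no overlap. ±3 days gives days 4-10, touching only day 10. With ±4 days or more, a visit can follow a day-10 staple removal.

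**The case against.** A window is an outer tolerance, not a forecast. Staff aiming at one week will rarely test on the day of surgery, so an even spread from day 0 overstates the scatter. This stands: the table permits the mixing but does not show that it will occur, and the upper end of the noise range should be read in that light.

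A reader might infer more from the window than the documents support:

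- **That timing scatter overwhelms a comparison of 20 per arm.** The low end of the calculation is an 8% loss, and the slope is assumed throughout.
- **That the arms will be seen on different days, creating a false treatment effect.** Patients are randomized and both arms follow one visit schedule with the study coordinator. The 3-day shift above is hypothetical, and no mechanism for it appears in the documents.
- **That a third of the brace arm is tested after resuming the brace.** One third is the share of permitted days. The same even-spread assumption gives 13-20% of visits. Brace wear is also the assigned treatment, so a difference in wear between arms is not in itself confounding. The problem is that the plan does not record it or say what this visit is meant to measure.
- **That the main comparison is compromised.** The zero-month time point may well be the pre-operative one, paired with the 12-week visit, and then this visit lies outside that comparison. It may also be this first post-operative visit. The text does not settle it.

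It is also fair to say that the covariate list is open-ended, so visit day could be added. But the day has to be recorded first, and nothing provides for that.

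**Conclusion.** The point holds in a limited form. That the window runs from day 0 to day 14 and overlaps the brace's return follows directly from the documents' own figures. Its main consequence is extra noise at one visit: 8-43% of the information, against about 1-6% with days 5-9, given a slope of 0.5-1.5 SD per week and evenly spread visits. Mixed brace status is the smaller part: 13-20% of brace-arm visits under even spread, none if visits cluster on days 5-9, and 25-38% if all fall on days 7-14.

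Bias is conditional on visit timing differing by arm, and the documents give no sign of that. Early-recovery and time-to-normalized-function data are affected. An effect on the main comparison is possible but not established. The change is worth making because it is cheap, not because the trial fails without it.

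**What to change.** 1. Set a target assessment window of days 5-9 for this visit. It excludes the day of surgery and closes before the earliest staple removal.
2. Keep and analyse visits outside the target; do not count them as missed. This matters: at a slope of 0.5 SD per week, information per visit rises only from about 92% to 99%, so discarding 2 of 20 visits per arm (0.90 × 99% = 89%) would more than cancel the gain.
3. Record the actual post-operative day, whether the brace had been resumed, and whether it was worn during testing.
4. Add post-operative day to the GLM for this visit, and report a sensitivity analysis without visits made after the brace's return. That analysis is supportive only, because it removes patients from one arm.
5. Reconcile the table's window with the no-brace statement in the visit list, and align the visit numbers, without changing when the brace is resumed. State which visit is the zero-month time point.

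The cost is a protocol wording change, somewhat tighter scheduling, a few extra data fields, and one extra covariate in a trial of 40.
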